16.0 OTHER THERAPY

All supportive therapy for optimal medical care will be given during the study period at the discretion of the attending physician(s) within the parameters of the protocol and documented as concomitant medication.

17.0 ADVERSE EVENTS (AE) AND SERIOUS ADVERSE EVENTS (SAE)

Data on all adverse events grade 2 or greater regardless of relationship to study treatment will be collected from the start of study treatment on day 1 and will continue to be collected for 30 days after the last Cetuximab and radiation dose. Adverse events believed related to treatment with Cetuximab and/or radiation will continue to be collected for 3 years following end of study treatment, as outlined on the study calendar, and captured as Late Adverse Events. Serious adverse events will continue to be followed until resolution or clearly determined to be due to a patient's stable or chronic condition or intercurrent illness(es). The investigator is responsible for the detection and documentation of events meeting the criteria and definition of an AE or SAE as provided in this protocol. During the study, when there is a safety evaluation, the investigator or site staff will be responsible for detecting AEs and SAEs, as detailed in this section of the protocol.

17.1 Definitions

The definitions of adverse events (AEs) and serious adverse events (SAEs) are given below. The following definitions of terms are guided by the International Conference on Harmonization and the US Code of Federal Regulations and are included here verbatim. It is the responsibility of the principal investigator to ensure that all staff involved in the trial is familiar with the content of this section.

17.1.1 Adverse Events (AE)

An AE is any untoward medical occurrence in a patient or clinical investigation subject administered a pharmaceutical product which does not necessarily have a causal relationship with this treatment. An AE can therefore be any unfavorable and unintended sign (including an abnormal laboratory finding), symptom, or disease temporally associated with the use of a medicinal (investigational) product, whether or not related to the medicinal (investigational) product.

Examples of an AE include:

- Significant or unexpected worsening or exacerbation of the condition/indication under study.
- Exacerbation of a chronic or intermittent pre-existing condition including either an increase in frequency and/or intensity (grade) of the condition.
- New conditions detected or diagnosed after investigational product administration even though may have been present prior to the start of the study.
- Signs, symptoms, or the clinical sequelae associated with a suspected interaction of the investigational product with a concomitant medication.
- Signs, symptoms, or the clinical sequelae associated with a suspected overdose of either investigational product or a concurrent medication.

Any medical condition or laboratory abnormality with an onset date before initial Cetuximab administration is considered to be pre-existing in nature.

Any known pre-existing conditions that are ongoing at time of study entry, and any events of Grade 3 or 4 severity that occur up to 30 days before study entry (even if resolved prior to study entry) should be considered medical history and recorded in the appropriate section of the case report form.

All adverse events grade 2 or greater occurring from initial investigational product administration through 30 days following the last dose of Cetuximab and/or radiation must be recorded as an adverse event in the patient's source documents and on the CRF regardless of frequency, severity (grade) or assessed relationship to Cetuximab and/or radiation.

In addition to new events, any increase in the frequency or severity (i.e., toxicity grade) of a pre-existing condition that occurs after the patient begins Cetuximab and radiation is also considered an adverse event.

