7.5.2 Research Biopsies

Two research biopsies will be obtained. These research biopsies will be delivered directly to the Radiation Oncology research laboratory. The pre-treatment research biopsy (5-10 mm³) will be taken prior to therapy to assess baseline EGFR pathway activation. This pre-treatment biopsy will be performed for research purposes if a suitable clinical biopsy specimen is not available. A clinical specimen will be suitable if the biopsy was performed at UMHS within 30 days of consent. The second biopsy will be obtained 7 days (+/- 2 days) after the loading dose of cetuximab and will be examined for changes in EGFR pathway activation. Both biopsies will be performed in the clinic, under local anesthesia, by an otolaryngologist or oral surgeon who is a co-investigator of the study. The second biopsy will only be obtained if it can be done without general anesthesia.

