11.0 STUDY CALENDAR

Assessment	Pre-Treatment*	Day 0 Loading Dose	Day 7 (+/- 2 days)	Weekly during Treatment†	12-14 wks post RT (+/- 1 month)	Follow Up ³
H&P/Physician Evaluation	X			X	X	X
Smoking status and tumor HPV or p16 determination	X					
Biopsy	X		X ¹			
Buccal swab	X		X ¹			
COMP, Mg	X			X	X	
CBCP with diff	X			X	X	
PET-CT	X				X ²	
Dental Evaluation	X					
Toxicity Evaluation	X			X	X	X
QOL Questionnaire	X				X	X
Videofluoroscopy	X				X	X
Cetuximab		X		X		

* The pre-treatment period is prior to the administration of the cetuximab loading dose

† Radiation therapy will start within 4 days following Day 7 biopsy

¹Research biopsy will be performed 7 days (+/- 2 days) after cetuximab. This second biopsy will only be obtained if it can be done without general anesthesia.

²Restaging PET-CT will be obtained at 12-14 weeks.

³Follow Up: Examinations will be performed as comparable to clinical practice: at 1 month after the completion of therapy and then every 2 months during years 1 and 2, and at 3-month intervals during year 3. Toxicity evaluation will be collected at each visit. Quality of Life Questionnaires will be given to patients at follow-up visits 1, 3, 6, 12, 18, 24 and 36 months. Videofluoroscopy will be performed at 3, 12, and 24 months after therapy. Allowable windows for all these time points are +/- 1 month.

Note: Once patients discontinue treatment (Section 13.0) or have tumor progression/recurrence, they will be followed as clinically indicated for 3 years following the completion of radiation and/or cetuximab.

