17.1.2 Serious Adverse Events (SAE)

A serious adverse event is an AE which occurs after the initial dose of Cetuximab, during treatment, or within 30 days of the last dose of cetuximab and/or radiation that fulfills one or more of the following criteria regardless of cause or assessed relationship to therapy.

Any untoward medical occurrence that at any dose:

- Results in death,

- Is life-threatening

NOTE: The term 'life-threatening' in the definition of 'serious' refers to any adverse drug experience that places the patient or subject, in the view of the investigator, at immediate risk of death from the reaction as it occurred, i.e., it does not include a reaction that, had it occurred in a more severe form, might have caused death.

- Requires inpatient hospitalization or prolongation of hospitalization

NOTE: In general, hospitalization signifies that the patient or subject has been detained (usually involving at least an overnight stay) at the hospital for observation and/or treatment that would not have been appropriate in the physician's office or out-patient setting. Complications that occur during hospitalization are AEs. If a complication prolongs hospitalization or fulfills any other serious criteria, the event is serious. When in doubt as to whether "hospitalization" occurred or was necessary, the AE should be considered serious. Hospitalization for elective treatment of a pre-existing condition that did not worsen from baseline is not considered an AE. Planned hospitalization for surgical procedures, either related or unrelated to the patients cancer is not considered a serious adverse event.

- Results in persistent or significant disability/incapacity

NOTE: The term disability means a substantial disruption of a person's ability to conduct normal life functions.

-Is a congenital abnormality/birth defect.

Or

- Important medical events

Events which may not result in death, be life-threatening, or require hospitalization may be considered a serious adverse drug experience when, based upon appropriate medical judgment, they may jeopardized the patient or subject and may require medical or surgical intervention to prevent one of the

outcomes listed in this definition.

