17.2.1.2 Serious Adverse Event Reporting Timeline

17.2.1.2.1 “Serious” adverse events which occur after the initial dose of Cetuximab, during treatment, or within 30 days of the last dose of Cetuximab or last fraction of radiation (including all deaths), MUST be reported immediately, i.e., within one day (24 hours) of being identified.

17.2.1.2.2 An initial written report of the serious adverse event must be prepared using the Medwatch or similar form, and submitted within 48 hours of awareness of event.

17.2.1.2.3 All fatal or life threatening serious adverse events must be reported IMMEDIATELY and then the initial SAE report submitted within 24 hours of awareness of event.

17.2.1.2.4 This report should provide a detailed description of the adverse event. Additional information (i.e. hospitalization records) will be submitted if requested by the IRB or other governing body, and include protocol number and patient assigned study number.

17.2.1.2.5 Copies of each report will be kept in the Investigator's File. The investigator will submit, on request, copies of all these reports to the relevant ethics committee.

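### Complications of the research-only pre-treatment biopsy that begin before the first cetuximab dose are classed as pre-existing and fall outside AE and SAE capture, unless they worsen or are first detected after dosing

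*Combined protocol and SAP*

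**What the plan says.** Section 7.5.2 plans two research biopsies. On the first it says: "This pre-treatment biopsy will be performed for research purposes if a suitable clinical biopsy specimen is not available". A clinical specimen counts as suitable only if it was taken at UMHS within 30 days of consent. The calendar in Section 11.0 lists a biopsy in the pre-treatment column and defines that column: "The pre-treatment period is prior to the administration of the cetuximab loading dose". The second research biopsy follows the loading dose by 7 days (+/- 2 days).

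The safety section sets its windows in four places:

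- Section 17.0, AE collection: data "will be collected from the start of study treatment on day 1".
- Section 17.1.1, AE recording: "All adverse events grade 2 or greater occurring from initial investigational product administration through 30 days following the last dose".
- Section 17.1.2, SAE definition: "A serious adverse event is an AE which occurs after the initial dose of Cetuximab, during treatment, or within 30 days".
- Section 17.2.1.2.1, expedited reporting: serious "adverse events which occur after the initial dose of Cetuximab, during treatment, or within 30 days".

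Section 17.1.1 also classifies what comes earlier: "Any medical condition or laboratory abnormality with an onset date before initial Cetuximab administration is considered to be pre-existing in nature".

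**The concern.** The pre-treatment research biopsy is invasive and, in the patients who need it, is done only for the study. It serves secondary objective 3.2.1, and Section 20.1 sets enrollment at 43 in order to obtain 36 patients who complete radiation and have both biopsies. If it causes harm, that harm is attributable to the research.

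Section 17.2.1.1 sends SAE reports to the IRB and the Principal Investigator and carries them into the Data and Safety Monitoring Report. An event that cannot be an SAE by definition does not enter that route. The safety rules would then label a study-caused complication as part of the patient's prior condition, and the IRB and monitoring board would not see it through SAE reporting.

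**Working it through.** No figure is at issue and no arithmetic beyond day counting applies. The check sets the timing of the two research biopsies against the four windows.

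**Timing.** Take the loading dose as Day 0 (Section 7.7.1). The first research biopsy falls before Day 0, and the interval from biopsy to dose is not fixed. The second falls between Day 7 - 2 = Day 5 and Day 7 + 2 = Day 9.

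**Outcome for each type of complication.**

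| Case | Complication | Treatment under Section 17 |
|---|---|---|
| a | First biopsy; onset before Day 0, recognized then, no later worsening | Pre-existing; not an AE or SAE, whatever its seriousness |
| b | First biopsy; onset before Day 0, worsens after treatment begins | The worsening is an AE (17.1.1) |
| c | First biopsy; onset before Day 0, first detected after dosing | Listed among the AE examples in 17.1.1 |
| d | First biopsy; onset after the first dose | Recorded if grade 2 or greater; an SAE if a serious criterion is met |
| e | Second biopsy (Day 5 to Day 9) | Inside the window; treated as in d |

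Case a is the gap. Cases a and e can be the same clinical event after the same kind of procedure, yet only e is captured.

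Case b has a small ambiguity. One sentence in 17.1.1 counts worsening once the patient has begun both cetuximab and radiation, and radiation starts after the Day 7 biopsy. The AE examples in the same section are broader, so I read worsening after the first dose as captured.

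**Does any other text close case a?**

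- Medical history (17.1.1) takes in conditions ongoing at study entry and Grade 3 or 4 events in the 30 days before entry. Study entry is not defined relative to the biopsy. If it means enrollment, an event between entry and first dose is not clearly covered. If it means first dose, a Grade 3 or 4 event might be recorded as history, but that is still not AE or SAE reporting.
- The relatedness definitions in 17.3 mention research interventions but set no collection window.
- The death rule at the end of 17.3 counts from the last study treatment and does not address death before any treatment.
- Baseline toxicity assessment (6.7) carries no AE or SAE reporting.
- Section 18.0 has the study committee discuss SAE/UaP reporting. UaP is not defined, and no route for pre-dose events is described.

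None of these opens an AE or SAE window before the first dose.

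**The case against.** The best defense is that the gap is narrow. The biopsy is small, done in the clinic under local anesthesia by an otolaryngologist or oral surgeon (7.5.2), in tumors already judged accessible there (4.9). Only patients without a suitable clinical specimen have it for research alone. The AE definition is product-based, and the protocol says it follows international and federal definitions (17.1). The study committee reviews participant safety and reports quarterly to an independent board under an institutional plan that is not part of these documents. All of this stands. It limits the likely number of events and prevents a firm conclusion that such harm would go unreviewed by every route. It does not give case a an AE or SAE route.

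A reader might also infer more than the text supports:

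- *That biopsy complications are never reported, or are all lost.* Cases b, c and d are captured.
- *That all 43 patients are exposed.* Nothing in the documents says how many lack a suitable specimen; 43 is only the planned enrollment.
- *That Section 17.3 contradicts the windows.* It grades causality. Its reference to research interventions already applies to the Day 7 biopsy and swab, which fall inside the window.
- *That reactions to the loading dose are missed because 17.0 says day 1 while 7.7.1 says Day 0.* The same sentence in 17.0 starts at study treatment, and 17.1.1 starts at first administration. This is a labelling slip.

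**Conclusion.** The concern holds for one defined class of events: complications of the research-only pre-treatment biopsy that begin before the first cetuximab dose and neither worsen nor are first detected afterwards. For these, the stated rule assigns the wrong category even when the event is serious. This is more than missing detail, because the sentence in 17.1.1 positively classes them as pre-existing.

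The size cannot be computed. It depends on the number of patients without a UMHS specimen taken within 30 days of consent, the complication rate of the biopsy, and the biopsy-to-dose interval; the documents give none of these. I expect few events. The conclusion rests on reading the four windows as written and on no separate consent-based window existing in the institutional monitoring plan, which was not available. No efficacy or toxicity analysis changes. The amendment is worth making because it is cheap and concerns harm from a procedure added for research.

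**What to change.** Amend Section 17 so that, for events related to research-only procedures, AE and SAE capture starts at the pre-treatment research biopsy. Exempt those events from the pre-existing sentence in 17.1.1 and from the conditions in 17.1.2 and 17.2.1.2.1 that require onset after the initial dose. The window for all other events can stay where it is.

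As an editorial correction, reconcile day 1 in 17.0 with Day 0 in 7.7.1.

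The cost is a few sentences in an amendment, an earlier CRF start for this class of event, and a few additional reports. Treatment, endpoints and sample size are unchanged.

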17.1.2 Serious Adverse Events (SAE)

A serious adverse event is an AE which occurs after the initial dose of Cetuximab, during treatment, or within 30 days of the last dose of cetuximab and/or radiation that fulfills one or more of the following criteria regardless of cause or assessed relationship to therapy.

Any untoward medical occurrence that at any dose:

- Results in death,

- Is life-threatening

NOTE: The term 'life-threatening' in the definition of 'serious' refers to any adverse drug experience that places the patient or subject, in the view of the investigator, at immediate risk of death from the reaction as it occurred, i.e., it does not include a reaction that, had it occurred in a more severe form, might have caused death.

- Requires inpatient hospitalization or prolongation of hospitalization

NOTE: In general, hospitalization signifies that the patient or subject has been detained (usually involving at least an overnight stay) at the hospital for observation and/or treatment that would not have been appropriate in the physician's office or out-patient setting. Complications that occur during hospitalization are AEs. If a complication prolongs hospitalization or fulfills any other serious criteria, the event is serious. When in doubt as to whether "hospitalization" occurred or was necessary, the AE should be considered serious. Hospitalization for elective treatment of a pre-existing condition that did not worsen from baseline is not considered an AE. Planned hospitalization for surgical procedures, either related or unrelated to the patients cancer is not considered a serious adverse event.

- Results in persistent or significant disability/incapacity

NOTE: The term disability means a substantial disruption of a person's ability to conduct normal life functions.

-Is a congenital abnormality/birth defect.

Or

- Important medical events

Events which may not result in death, be life-threatening, or require hospitalization may be considered a serious adverse drug experience when, based upon appropriate medical judgment, they may jeopardized the patient or subject and may require medical or surgical intervention to prevent one of the

outcomes listed in this definition.

17.2 Adverse Event Reporting Requirements

17.2.1 All Serious Adverse Events

17.2.1.1 Serious Adverse Event Reporting

Serious adverse events reports are submitted via the MedWatch form or similar form. The MedWatch report must be submitted to the University of Michigan IRB and to the Principal Investigator. AEs reported as Serious Adverse Events must also be reported in routine study data submissions including the Data and Safety Monitoring Report, in addition to the IRB.

17.2.1.2 Serious Adverse Event Reporting Timeline

17.2.1.2.1 “Serious” adverse events which occur after the initial dose of Cetuximab, during treatment, or within 30 days of the last dose of Cetuximab or last fraction of radiation (including all deaths), MUST be reported immediately, i.e., within one day (24 hours) of being identified.

17.2.1.2.2 An initial written report of the serious adverse event must be prepared using the Medwatch or similar form, and submitted within 48 hours of awareness of event.

17.2.1.2.3 All fatal or life threatening serious adverse events must be reported IMMEDIATELY and then the initial SAE report submitted within 24 hours of awareness of event.

17.2.1.2.4 This report should provide a detailed description of the adverse event. Additional information (i.e. hospitalization records) will be submitted if requested by the IRB or other governing body, and include protocol number and patient assigned study number.

17.2.1.2.5 Copies of each report will be kept in the Investigator's File. The investigator will submit, on request, copies of all these reports to the relevant ethics committee.

17.2.1.2.6 Serious Adverse Event (SAE) Reporting Follow-up
Follow-up information will be submitted to the IRB following instructions above and within 7 days of becoming available.

17.2.2 Clinical Laboratory Abnormalities and Other Abnormal Assessments as AE's and SAE's

Abnormal laboratory findings (e.g., clinical chemistry and hematology) or

other abnormal assessments (e.g., ECGs) that are judged by the investigator as clinically significant will be recorded as AEs or SAEs if they meet the definitions as defined in Section 17.1. Clinically significant abnormal laboratory findings or other abnormal assessments that are detected during the study or are present at baseline and significantly worsen following the start of the study will be reported as AEs or SAEs. However, clinically significant abnormal laboratory findings or other abnormal assessments that are associated with the disease being studied, unless judged by the investigator as more severe than expected for the patient's condition, or that are present or detected at the start of the study and do not worsen, will not be reported as AEs or SAEs. The investigator will exercise his or her medical and scientific judgment in deciding whether an abnormal laboratory finding or other abnormal assessment is clinically significant.

17.2.3 Disease-Related Events and/or Disease-Related Outcomes Not Qualifying as SAEs

“Lack of efficacy” per se will not be reported as an AE. The signs and symptoms or clinical sequelae resulting from lack of efficacy will be reported if they fulfill the AE or SAE definition (including clarifications). Progressive disease found by scan or on clinical evaluation should be captured but not as an AE.

17.2.4 If a subject begins another therapy for their disease (outside of a surgical intervention to remove their disease), the patient will be considered off study and adverse events will no longer be collected on this subject.

17.2.5 Grading of Adverse Events

The severity of all adverse events and laboratory abnormalities will be graded according to the US National Cancer Institute’s Common Terminology Criteria for Adverse Events version 4.0 (CTCAE).

17.3 Relationship to Cetuximab and Radiation

Related Event: Any adverse event that has a temporal relationship to the administration of the investigational drug or research intervention, follows a known or suspected pattern of response, and for which an alternative cause may not be present, is definitely, probably, or possibly associated with the investigational drug/agent. Investigator needs to judge relatedness and be prepared to justify the judgment.

- Definitely Related: The adverse event is clearly related to the investigational agent(s) or research intervention: the adverse event has a temporal relationship to the administration of the investigational agent(s) or research intervention, follows a known pattern of response, and no alternative cause is present.
- Possibly Related: There is a reasonable possibility that the event may have been caused by or is linked in a significant way to the research; the adverse event has a temporal relationship to the administration of the investigational agent(s) or research

intervention, follows a suspected pattern of response, but an alternative cause is present.

- Probably Related: The adverse event is likely related to the investigational agent(s) or intervention: the adverse event has a temporal relationship to the administration of the investigational agent(s) or research intervention, follows a known or suspected pattern of response, but an alternative cause may be present.
- Unlikely to be related: The adverse event is doubtfully related to the investigational agent(s) or intervention: the adverse event has a temporal relationship to the administration of the investigational agent(s) or research intervention, but follows no known or suspected pattern of response, and an alternative cause is present.
- Unrelated (or Not Related): The adverse event is clearly NOT related to the investigational agent(s) or intervention: the adverse event has no temporal relationship to the administration of the investigational agent(s) or research intervention, follows no known or suspected pattern of response, and an alternative cause is present.

Death: Deaths occurring within 30 days of the last study treatment are reportable events regardless of whether or not the investigators deem the death to be related to the study. If death occurs later than 30 days after the last study treatment AND the subject is still onstudy (i.e. subject would have had further follow-up or intervention/interaction had death not occurred), then the death may still be a reportable event. If the subject is NOT still on-study and there is no long-term follow-up, a late death does not need to be reported the IRBMED even if the investigator learns that the subject died.

